5.2 Protection of Participant Privacy

Patient Privacy – During this study, non-invasive wearable devices will be provided to patients to collect continuous physiologic data. PhysIQ's solution, including wearable patches, mobile device and Microsoft Azure cloud platform comply with the administrative safeguards and implementation specifications described in 45CFR§164.308, with respect to HIPAA. No PHI will be uploaded to the physIQ platform.

The physiological data upload via digital cellular network is secured with TLS cryptographic protocol between the mobile phones and the server. The physIQ platform is securely hosted in the Google cloud. The physIQ cloud stores the raw physiological telemetry data captured by the study device, and also stores analytical results generated by running that raw data through the physIQ Analytics Modules. All the telemetry and analytical results are stored separately from any personally identifiable information (PII) that an institution might choose to enter in the system. There is no requirement to enter PII to use the platform, as all data can be tracked solely by random ID as well. PHI will not be transmitted to physIQ for this process and the only data that will be transmitted is a random study ID generated at NorthShore. NorthShore will maintain the key to the identifier. The data can only be obtained or viewed via secure authenticated login.

The physiologic, alert, and patient reported status data will be transferred back to NorthShore for storage using a sFTP. Data from wearable devices and physIQ platform and EHR data from NorthShore will be linked, deidentified using standard NorthShore protocol prior to transfer to CMU via secure FTP. There is an existing Data Use Agreement in place between NorthShore and Carnegie Mellon University (CMU) which will be renewed for this project. Only the PI at NorthShore and Co-PI at CMU will have access to the sFTP site. Only named study personnel will have access to data. PhysIQ will not have access to any PHI. NorthShore and CMU will delete all data after study termination.

DEVICE INFORMATION

COMPANY ADDRESS: physIQ, Inc.

[name]
[name]

6.1 DEVICE DESCRIPTION:

The pinpointIQ Solution is a wireless remote patient monitoring system intended for use by healthcare professionals for continuous collection of physiological data in home and healthcare settings. The pinpointIQ Solution consists of clinical-grade wearable sensors such as the VitalPatch™ Sensor (a 510k-cleared disposable patch with integrated biosensors and a wireless transceiver) and the physIQ Platform (a mobile application for secure data transmission, cloud-based information-technology [IT] infrastructure, physiology analytics modules, and clinician user interface). The patch is worn on the torso for up to 5 days and measures and records physiological variables that can include, but are not limited to, electrocardiography (ECG), vital signs and activity. Data are transmitted wirelessly from the VitalPatch™ Sensor to the physIQ cloud for storage and analysis and presentation within the clinician user interface.

INVESTIGATIONAL DEVICE:

Device Description

PinpointIQ is a wireless remote monitoring system intended for use by healthcare professionals for continuous collection of physiological data in home and healthcare settings. PinpointIQ consists of:

- VitalPatch™ Sensor (chest-worn disposable biosensor patch)
- Mobile application (“app”) for secure data transmission
- Cloud-based IT infrastructure
- Physiology Analytics modules, comprising:
 - Personalized Physiology Analytics
 - Vital Sign Feature Analytics
 - Heart rhythm analytics
 - Actigraphy analytics
 - Clinician-defined rules
- Browser-based clinician user interface

Biosensors

Vital Connect VitalPatch

VitalPatch™ (Vital Connect Inc) is an FDA 510(k)-cleared, wearable adhesive Band-Aid-like multi-sensor device which will be used to stream and collect continuous vital sign data from patients. The device is a disposable adhesive patch with an integral one-time-use battery and integrated electronics. The battery life of each disposable adhesive patch lasts about 7 days.

The VitalPatch™ is generally applied to the skin of the patient’s left upper chest (worn diagonally on the chest above the heart or laterally on the rib cage just below the heart). Further VitalPatch™ description

and instructions for that application are shown in an attached document. VitalPatches™ can be worn continuously, including in the shower. VitalPatches™ should be replaced when adhesion or the battery fails. In addition, physIQ recommends considering the use of UNI-SOLVE wipes to assist in the removal of the VitalPatch™.

6.2 Data Transport via physIQ Android Mobile App and physIQ Platform

The physIQ Android mobile app is loaded onto an Android-based phone or tablet mobile device. The mobile device offloads vital sign data from the VitalPatch™ (via low energy Bluetooth) and uploads it using digital cellular or WiFi network to the cloud-based server. In addition to transmitting physiological data, the app also may present questionnaires to the patient that are answered directly within the app.

Upload via digital cellular network is secured with TLS cryptographic protocol between the mobile phones and the server. The physIQ platform is securely hosted in the Google cloud. The physIQ cloud stores the raw physiological telemetry data captured by the study device, and also stores analytical results generated by running that raw data through the physIQ Analytics Modules. All the telemetry and analytical results are stored separately from any personally identifiable information (PII) that an institution might choose to enter in the system. There is no requirement to enter PII in order to use the platform, as all data can be tracked solely by random ID as well. PHI will not be transmitted to physIQ for this process and the only data that will be transmitted is a random ID generated at NorthShore. NorthShore will maintain the key to the identifier. The data can only be obtained or viewed via secure authenticated login.

6.3 Analytics

The study will utilize physIQ's multivariate analytical methods that learn the behavior of an individual patient's vital signs at a baseline, and then detect changes in the behavior of the vital signs compared to the baseline. Changes in vital signs relationships may be indicative of current or future important clinical events. These changes are indicated through the Multivariate Change Index ("MCI"), which is a scalar index between 0 and 1, where values close to 0 indicate no significant change from baseline and values close to 1 indicated greater changes from baseline.

Additional "feature" analytics include atrial fibrillation detection, arrhythmia (ectopic beat) burden, Cheyne-Stokes respiration, sleep quantification, and walking detection. Clinician-defined rules include applying thresholds to time series vital signs, sleep fragmentation, tachycardia, bradycardia, A-Fib with RVR, elevated respiration rate, and long-duration horizontal posture.

6.4 Regulatory Status

This study is considered a non-significant risk (NSR) Investigational Device Exemption (IDE) study according to 21 CFR §812.2(b) to evaluate the clinical utility of PhysIQ vital patch solution. All FDA-cleared devices in pinpointIQ will be used according to their intended use. The components of this system and clearance status are described below:

1. VitalPatch wearable biosensor: FDA 510k-cleared Class II-regulated medical device – Vital Signs Biosensor (K190916)
2. PhysIQ Cloud-based IT platform (physIQ mobile app, IT platform, Clinician User Interface): FDA Class I-regulated medical device – Medical device data system

3. PhysIQ Personalized Physiology Analytics: FDA 510k-cleared Class II-regulated medical device – Multivariate Change Index ([K142512](#))
4. PhysIQ feature analytics: FDA 510K cleared Class II-regulated medical device – heart rate, heart rate variability, respiration rate and atrial fibrillation detection ([K183322](#))
5. PhysIQ actigraphy analytics: FDA Class-I-regulated medical device – walking, steps, posture, sleep, body tilt, gross activity, activity stratification.

- **Potential Risks and Benefits**

When used in accordance with the clinical protocol, risks associated with pinpointIQ are considered low. To ensure proper use of the solution, subjects, patients and providers will be trained in accordance with the manufacturer's instructions for use. In addition, clearly defined study eligibility criteria have been established to ensure that only appropriate patients are enrolled in the study.

The potential risks of VitalPatch may include the following: adverse skin reactions, skin irritations, mild soreness, redness (see attached IFU).

- **Device Packaging, Labeling and Use**

The VitalPatch™ and mobile phone will be shipped as a kit to NorthShore in the care of the PI/research coordinator. Device components will be labeled "For Prescribed Use in a Clinical Trial" and packaged by physIQ according to applicable regulations. Upon completion of data collection, the subject will mail back all study equipment in a pre-paid mailer that was provided in the kit. PhysIQ and NorthShore research team will maintain device accountability records for each study site and for each subject enrolled, pursuant to 21 CFR§812.110 and Good Clinical Practices (GCP).

BIBLIOGRAPHY

1. Hospital Readmission Reduction Program, Patient Protection and Affordable Care Act, Vol [S]3025 2010

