After discharge, CHF patients will be asked two questions every morning from the pinpoint IQ application. The pinpoint IQ platform will query patients about their current weight and if they actively have symptoms. These symptoms include chest pain, shortness of breath at rest, lightheadedness, dizziness, passing out, lower extremity swelling, orthopnea and postural nocturnal dyspnea. The monitoring nurse will evaluate the pinpoint IQ in the morning after the patient has filled out the questionnaire. They will evaluate the responses to the questions and the physiologic alerting system built by physIQ. There will be an algorithm built within physIQ's system that provides an alert to the monitoring nurse if the criteria from Table 1 are met.

Patients 1-5:
Any positive symptom
Example Question: Do you have any of the following symptoms? (multi-choice)
a. Chest pain b. Shortness of breath at rest c. Lower extremity edema d. Orthopnea (not able to lay flat) e. PND (Waking up in the middle of the night short of breath) f. Syncope (Passing out) g. Fatigue h. Vomiting i. Diarrhea
5 lb weight gain over dry weight (
Example Question:
What is your dry weight? What is your weight today?
A high risk alert
A predefined number of standard alerts in a day + 1-4 lb weight gain over dry weight

Table 1: Phase 1, physIQ alerts system for monitoring nurse for CHF

The actual thresholds for the high-risk alerts and the number of standard alerts may be changed from patient to patient based on how each case progresses and the density and frequency of alerts. Determining the optimal thresholds for these two types of alerts will be a key aim of phase 2. The goal is to maximize signal while minimizing noise.

If any of these conditions listed in Table 1 are met, the monitoring nurse will call the patient and go through a predefined note with the following data elements and questions.

monitoring nurse Alert System – CHF, phase 1

Do you currently have the following symptoms? (y/n)

- **Chest pain**
- **Shortness of breath at rest**
- Lower extremity edema
- Orthopnea (not able to lay flat)
- PND (Waking up in the middle of the night short of breath)
- **Syncope (Passing out)**
- Fatigue
- Vomiting
- Diarrhea

(Any Red Bolded symptoms results in phone call to clinical team and may physically see patients at home)

What is your dry weight? (Can look up patient's discharge weight and fill in or automate with data element)

What is your weight today? (Free text)

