In addition, the monitoring nurse will double the diuretic dosing if a patient has new symptoms of shortness of breath at rest, orthopnea, postural nocturnal dyspnea, or lower extremity swelling. The double diuretic dosing will also occur if weight gain increases by ≥ 5 lbs over dry weight. If the symptom question is met, then the patient will get a 3rd question on Day n+1 that asks if the symptoms are getting better, worse or the same. If the symptoms are getting worse, the monitoring nurse will escalate to the clinical care team with a phone call. If the symptoms are getting better or are the same, the double dose of diuretic will remain unchanged. If symptoms or weight gain normalize, the double dose of diuretic will be deescalated to the standard dosing regimen.

If there is a high-risk alert, then the monitoring nurse receives an alert, which will result in a phone call to the patients and note template with patients. The monitoring nurse alert will also occur if there are a certain number of alerts (to be determined and varied during patients 1-5) and 1-4 lbs of weight gain (to be determined and varied during patients 1-5). In addition, if patients have some combination of weight gain and standard alerts or a high-risk alert, then the doubling of diuretics will also occur. If patients have a combination of 1-4 lb weight gain and a set number of device alerts, we will stop diuretic dosing if weight gain normalizes back to dry weight. The process map for patients 1-5 is shown in Figure 1. Escalating and deescalating diuretic dosing will also be built into the same note template in addition to prompts for education to ensure a standardized process from the monitoring nurses. We also have a multiple-choice option for monitoring nurse to document the care plan for participants.

[figure not shown]

Figure 1: Process map for CHF Patient 1-5

If care is escalated to the clinical care team which includes Advanced Practice Nurses, Physician Assistants and Physicians, the care team will pursue various interventions including counseling, altering medication therapy, urgent visits to heart failure clinic ideally within 72 hours, and if no other available options readmission. These workflows will be left to the discretion of the clinical care team given the nuance in taking care of these high-risk patients and the existing relationship and prior history with

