these providers. There are some standardized workflows that will be followed by the care team that are of note. If the patient has diuretic dose escalated for 3 days, then the clinical care team will make sure patient has a basic metabolic panel ordered to make sure patient's renal function is stable on the higher diuretic dose. We created a standardized note template for mid-level providers as part of the escalation pathway (Table 3). Also, all messaging from the monitoring nurse will be forwarded to the heart failure clinical pool and/or CHF APP pool per protocol to create the most rapid response back to the patient if required.

Cardiovascular symptoms not related to CHF Is the patient having any concerning cardiovascular symptoms not related to CHF? (y/n)
Pulmonary symptoms Is the patient having any concerning pulmonary symptoms not related to CHF? (y/n)
Infectious symptoms Is the patient having any symptoms concerning for an infection (eg: fever, dysuria, productive cough, diarrhea, vomiting, rash, or flu-like symptoms)? (y/n)
Urine output Does the patient have decreased urine output or are they not responding to their diuretic dose? (y/n)
Hematologic symptoms (such as bleeding and thrombosis) Is the patient having any concerning hematologic symptoms? (y/n)
Medication adherence questions 
 • In the last week has the patient missed any diuretic doses (eg: lasix, bumex, spironolactone)? (y/n/na) • In the last week has the patient missed any beta blocker doses (eg: metoprolol, carvedilol)? (y/n/na) • In the last week has the patient missed any ACE/ARB doses (eg: enalapril, lisinopril, benazepril, captopril, quinapril, irbesartan, losartan, olmesartan, valsartan)? (y/n/na)
Self-Care 
 1. Did the patient ask any questions related to self-care? (y/n) 2. Did a family member or caregiver ask any questions related to self-care? (y/n) 3. Did the patient or a family member or caregiver know their medications? (y/n) 4. What led to your communication with the patient? (monitoring nurse recommendation, patient called, abnormal lab finding, other)
Assessment 
 1. What do you think is the cause of the patient's decompensation? (HF exacerbation, cardiovascular non-HF, pulmonary, infectious, renal, other) 2. On a scale of 1 to 5 how confident are you in this choice? 1 being least confident, 5 being extremely confident (select number 1-5 from drop down menu)

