4.6 Retrospective Cohort Comparison

We will analyze and compare readmission metrics and care escalation process measures against a usual care retrospective control sample of patients. We will include patients who meet the same inclusion and exclusion criteria from 36 months prior to the start of the study to determine which process measures may be valuable in informing the design and deployment of remote monitoring of HF patients at scale in the future.

We are asking for a waiver for the retrospective cohort, as this contains minimal risk to the cohort. The data scientist and research coordinator will use EDW to look up and perform chart reviews for patients meeting the criteria for the retrospective cohort. All data will be de-identified and stored on the collaboration portal. Only the PI, data scientist, and research coordinator will have access to the data at NorthShore. Deidentified data will also be provided to Carnegie Mellon University to conduct the

predictive analytics sub aim as detailed in this protocol. This data will be deidentified when provided and a DUA will be requested for this work. All data will be destroyed upon completion of the study by the data scientist and by Carnegie Mellon University.

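### Section 6.4 names only skin effects of the patch as risks, although the pathway has the nurse double diuretics, and no aim or comparison uses the available data as a safety outcome for that escalation

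*Protocol*

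**What the plan says.** **Risk statement (protocol 6.4, potential risks and benefits).** The section opens with "When used in accordance with the clinical protocol, risks associated with pinpointIQ are considered low". The only risks it then names are those of the patch: "The potential risks of VitalPatch may include the following: adverse skin reactions, skin irritations, mild soreness, redness (see attached IFU".

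**Pathway (protocol 2.2, Table 2 and the text after it).** Escalation of diuretics is part of what is being tested. On symptoms, "the monitoring nurse will double the diuretic dosing if a patient has new symptoms of shortness of breath at rest", and likewise for orthopnea, nocturnal dyspnea or leg swelling. A gain of 5 lb or more over dry weight is also a trigger. Device output can be one too: "if patients have some combination of weight gain and standard alerts or a high-risk alert, then the doubling of diuretics will also occur". The alert settings are not fixed: "The actual thresholds for the high-risk alerts and the number of standard alerts may be changed from patient to patient".

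**Renal check (protocol 2.2).** Once a dose has been escalated for 3 days, the care team sees to it that a basic metabolic panel is ordered, to confirm that "renal function is stable on the higher diuretic dose".

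**Aims and comparison (protocol 2.1 and 4.6).** The aims cover thresholds, workflows, risk prediction, care processes, return on investment, effectiveness, feasibility and efficiency. None concerns safety. For the retrospective usual-care sample, the plan is: "We will analyze and compare readmission metrics and care escalation process measures".

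**Data at hand (protocol 4.3.1, item 4; Tables 2 and 3).** Consent gives access to labs, medications, notes, readmissions and mortality over 30 days. Table 2 records syncope, vomiting and diarrhea. Table 3 records urine output, a renal cause of decompensation, and decreasing or holding the diuretic.

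**The concern.** The study both runs the escalation rule and tunes the alert thresholds that feed it. Section 2.2 says that what is learned from 20 patients will set the phase 3 process. A threshold that fires more often produces more doubled doses. Any benefit would appear in readmission. A cost such as a creatinine or potassium change, or volume depletion treated without admission, has no designated place in the results. Thresholds could then be carried forward on readmission and process measures alone.

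The risk statement has the same gap. Its assurance depends on use under the clinical protocol, so it takes in the pathway, yet the hazard that section 2.2 itself checks for is not mentioned.

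**Working it through.** The protocol gives no figure for this point, so most of the check is textual.

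**1. Is alert-driven treatment within the scope of 6.4?** The low-risk statement is about the whole system used under the clinical protocol, and that protocol includes the doubling rule. The list of risks is about the patch alone. The list is therefore narrower than the statement it supports.

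**2. Is the hazard recognised elsewhere?** Yes. The stated purpose of the panel in 2.2 is renal stability on the higher dose. The panel is a care step, and no analysis of its result is described.

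**3. Which data could show harm, and how are they used?**

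| Item | Where recorded | Named as a safety outcome in 2.1 or 4.6? |
|---|---|---|
| Readmission | 4.3.1 item 4; compared in 4.6 | No; it is the efficacy measure, though severe harm would count in it |
| Mortality | 4.3.1 item 4 | No |
| Labs, medications, notes | 4.3.1 item 4 | No |
| Syncope, vomiting, diarrhea | Table 2 | No |
| Urine output, renal cause, held or decreased diuretic | Table 3 | No |
| Metabolic panel after 3 days | 2.2 | No |

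**4. Is exposure to the doubled dose well defined?** Not yet, because the de-escalation wording differs. Table 2 requires both absence of symptoms and return to dry weight. The text after it accepts normalisation of symptoms or weight. A later sentence, on 1-4 lb gain with device alerts, speaks of stopping diuretic dosing, where the others speak of returning to the discharge or standard dose. The end of a doubled-dose episode therefore depends on which sentence is read.

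**5. Exposure.** The rule is written out for phase 1, patients 1-5 (2.2): 5 x 30 = 150 patient-days. If it carries over to all 20 patients in 4.3.1 (assumption): 20 x 30 = 600. The share of days on a doubled dose is not given. At an assumed 10-30%, it would be 15-45 of 150 days, or 60-180 of 600.

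**6. What could a harm outcome show?** With zero events in n patients, the exact two-sided 95% upper limit is 1 - 0.025^(1/n). For n = 20 this is 1 - 0.025^(0.05) = 0.168, or 16.8%. The chance of at least one event is 1 - (1 - p)^n; the rates p are assumed, as the protocol gives none.

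| Assumed p | n = 5 | n = 20 |
|---|---|---|
| 2% | 10% | 33% |
| 5% | 23% | 64% |
| 10% | 41% | 88% |
| 15% | 56% | 96% |

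**7. How firm could an effectiveness claim be?** The inputs are the 15-30% readmission rate in 1.2, an assumed halving, an assumed two-sided alpha of 0.05, and 20 patients against an assumed 100 to 1000 controls. The normal approximation for two proportions (standard error pooled under the null, unpooled under the alternative) gives power of about 9% for 15% to 7.5%, and 24-26% for 30% to 15%.

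**The case against.** The other side has several good points.

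- **The quoted sentence is true of the patch.** It sits in a device section and defers to instructions for use that are not in the document. This stands: the fault is what 6.4 leaves out.
- **Harm is not invisible.** A reader might infer that no outcome captures it. The documents do not support that. Readmission is not limited to heart failure causes in 2.1 or 4.6, so severe over-treatment counts against the pathway. Syncope triggers a call to the clinical team, and labs and notes are accessible. What is missing is a designated outcome and its analysis.
- **Participants may have been told.** One might infer that they were not. The consent pages are not in the text reviewed, so this cannot be said.
- **An SAP may define safety tables, and 4.6 may not be exhaustive.** Section 3.2 mentions unscheduled visits as a process measure, so some contacts may be counted. This stands in part. The detail of tables can wait for an SAP. The risk statement, the aims and the named comparison are protocol content, and an SAP would not repair 6.4.
- **The study is a small pilot.** The power figures make a confirmatory finding of effectiveness unlikely. This also stands, and it moves the weight of the point to threshold tuning and the risk statement.
- **The 3-day lab rule is a clinical matter.** Agreed; nothing here asks for it to change.

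**Conclusion.** The point holds in a limited form, at moderate severity; it is not a must-fix. The visible risk text in 6.4 is narrower than the pathway in 2.2. The data that could show harm from diuretic escalation are not used for that purpose in the aims or in 4.6. As written, over-treatment short of readmission or death does not enter the effectiveness or threshold conclusions.

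The size is 150 patient-days of documented exposure. The figure of 600 rests on the assumption that the rule applies unchanged to all 20 patients. Any harm result will be descriptive, given the 16.8% limit after 0/20.

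Two further readings go too far. Calling this the study's main hazard is a judgement, since the documents rank no hazards. Saying that the study is bound to declare the pathway effective while blind to harm ignores both the low power and the harm-related items already recorded.

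**What to change.** 1. **Section 6.4:** state that the tested pathway includes protocol-driven diuretic changes, and name their risks, so that it agrees with 2.2.
2. **Section 4.6:** add a descriptive harm set within 30 days, from data that consent already covers: change in creatinine and potassium from discharge, recorded syncope, and ER or hospital contact for volume depletion.
3. **Reporting:** show it by doubled-dose exposure, with the number of patients who had a lab and exact intervals. Exposure can be taken from the escalate and de-escalate entries in the Table 2 plan field.
4. **Controls:** pull the items that the data warehouse holds. The Table 2 and 3 note items will not exist for controls. Labs may also be drawn more often in escalated patients, so the number tested must stand beside each lab result.
5. **Section 2.2:** reconcile the differing de-escalation wording so that doubled-dose exposure has one definition. The investigators must decide which wording applies; no dose or clinical rule is proposed here.

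The cost is protocol wording and a few extra data fields. The downside is that labs are unscheduled, so the harm data will be incomplete, dependent on who was tested, and descriptive only.
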